5.1.1. Procedures for Breaking Treatment Codes

In the event of a medical emergency where breaking the blind is required to provide medical care to the subject, the investigator may obtain treatment assignment directly from the IXRS system for that subject. Gilead recommends but does not require that the investigator contact the Gilead medical monitor before breaking the blind. Treatment assignment should remain blinded unless that knowledge is necessary to determine subject emergency medical care. The rationale for unblinding must be clearly explained in source documentation and on the case report form/ electronic case report form (CRF/eCRF), along with the date on which the treatment assignment was obtained. The investigator is requested to contact the Gilead medical monitor promptly in case of any treatment unblinding.

Blinding of study treatment is critical to the integrity of this clinical trial and therefore, if a subject's treatment assignment is disclosed to the investigator, the subject will have study treatment discontinued. All subjects will be followed until study completion unless consent to do so is specifically withdrawn by the subject.

Gilead Drug Safety and Public Health (DSPH) may independently unblind cases for expedited reporting of suspected unexpected serious adverse reactions (SUSARs).

5.2. Description and Handling of Tenofovir Alafenamide (TAF) and TDF

5.2.1. Formulation

5.2.1.1. Vemlidy® (Tenofovir Alafenamide [TAF] Tablets)

Vemlidy® (TAF) 25 mg tablets contain 28 mg of tenofovir alafenamide fumarate, which is equivalent to 25 mg of Vemlidy® (tenofovir alafenamide [TAF]). The tablets are yellow, round-shaped, and film-coated. The tablets are debossed with "GSI" on one side and "25" on the other side. In addition to the active ingredient, each film-coated tablet contains the following

inactive ingredients: lactose monohydrate, microcrystalline cellulose, croscarmellose sodium, magnesium stearate, polyethylene glycol, polyvinyl alcohol, talc, titanium dioxide, and yellow iron oxide.

5.2.1.2. Placebo to Match TAF Tablets

Placebo tablets to match TAF 25 mg are yellow, round-shaped, and film-coated. The tablets are debossed with "GSI" on one side and "25" on the other side. Each tablet contains the following inactive ingredients: lactose monohydrate, microcrystalline cellulose, croscarmellose sodium, magnesium stearate, polyethylene glycol, polyvinyl alcohol, talc, titanium dioxide, and yellow iron oxide.

5.2.1.3. Tenofovir Disoproxil Fumarate (Viread[®], Tenofovir DF, TDF)

TDF 300 mg tablets contain 300 mg of tenofovir disoproxil fumarate (TDF), which is equivalent to 245 mg of tenofovir disoproxil. The tablets are light blue, almond-shaped, plain-faced, and film-coated. Each tablet contains the following inactive ingredients: microcrystalline cellulose, lactose monohydrate, pregelatinized starch, croscarmellose sodium, and magnesium stearate. The film coating contains lactose monohydrate, hypromellose (hydroxypropyl methylcellulose), glycerol triacetate, titanium dioxide, and indigo carmine aluminum lake.

5.2.1.4. Placebo to Match TDF Tablets

Placebo tablets to match TDF 300 mg are light blue, almond-shaped, plain-faced, film-coated tablets. Each tablet contains the following inactive ingredients: denatonium benzoate, lactose monohydrate, pregelatinized starch, croscarmellose sodium, and magnesium stearate. The film coating contains the following inactive ingredients: lactose monohydrate, hypromellose (hydroxypropyl methylcellulose), triacetin, titanium dioxide, and indigo carmine aluminum lake.

5.2.2. Packaging and Labeling

TAF, TDF, and their matched placebo tablets are packaged in white, high density polyethylene (HDPE) bottles. Each bottle contains 30 tablets and a silica gel desiccant and polyester packing material. Each bottle is enclosed with a white, continuous thread, child-resistant polypropylene screw cap with an induction-sealed and aluminum-faced liner.

Study drug(s) to be distributed to centers in the US and other participating countries shall be labeled to meet applicable requirements of the FDA, EU Guideline to Good Manufacturing Practice – Annex 13 (Investigational Medicinal Products), and/or other local regulations.

5.2.3. Storage and Handling

TAF, TDF, and their matched placebo tablets should be stored at controlled room temperature of 25°C (77°F); excursions are permitted between 15°C and 30°C (59°F and 86°F). Storage conditions are specified on the label. Until dispensed to the subjects, all bottles of study drugs should be stored in a securely locked area, accessible only to authorized site personnel.

To ensure the stability and proper identification, study drug(s) should not be stored in a container other than the container in which they were supplied.

Consideration should be given to handling, preparation, and disposal through measures that minimize drug contact with the body. Appropriate precautions should be followed to avoid direct eye contact or exposure when handling.

5.3. Dosage and Administration of Tenofovir Alafenamide (TAF) and TDF

Subjects will be randomly assigned (1:1) to receive one of the following treatments in a blinded fashion:

- Treatment Arm A: approximately 230 subjects administered TAF 25 mg QD and matched placebo of Tenofovir DF (TDF) 300 mg QD
- **Treatment Arm B:** approximately 230 subjects administered Gilead-provided TDF 300 mg QD and matched placebo of TAF 25 mg QD

It is preferred that subjects take their study drug according to a morning dosing schedule; however, evening dosing is allowable.

All study drugs should be taken at approximately the same time each day with or without food. Subjects taking TDF 300 mg QD with food prior to randomization should continue to take study drug with food; subjects taking TDF 300 mg QD without food prior to randomization should continue to take study drug without food during the study period.

Study drug should be administered after assessing adverse events and concomitant medication(s).

5.4. Prior and Concomitant Medications

Concomitant/previous medications taken within 30 days of screening, up to and including the date of the last study visit, need to be recorded in the source documents and eCRFs.

The following medications are excluded while subjects are participating in the study. These medications are prohibited during the screening period and for a minimum of 30 days prior to the Baseline/Day 1 visit through the end of treatment:

- Investigational agents or devices for any indication
- Nephrotoxic agents (e.g., aminoglycosides, amphoterecin B, vancomycin, cidofovir, foscarnet, cisplatin, pentamidine, cyclosporine, tacrolimus)
- Probenecid

- Agents that reduce renal function or compete for active tubular secretion with tenofovir (e.g., cidofovir, acyclovir, valacyclovir, ganciclovir, valganciclovir)
- Systemic chemotherapeutic agents, systemic corticosteroids (except short-term use of prednisone as a steroid burst [≤ 1 week of use], immunosuppressant, or immunomodulating agents

Concomitant use of certain medications or herbal/natural supplements (inducers of drug transporters i.e., P-gp) with study drug(s) may result in PK interactions.

Examples of representative medications which are prohibited from 21 days prior to Day 1 through the end of treatment are listed below:

Table 5-1. Disallowed Concomitant Medications

Medication Class	Prohibited Medications	
Anticonvulsants	Carbamazepine, Oxcarbazepine, Phenobarbital, Phenytoin: may lower concentration of TAF and/or TFV	
Antimycobacterials	Rifapentine, Rifabutin, Rifampin	
Herbal/Natural Supplements	St. John's Wort, Echinacea, Milk thistle (i.e., silymarin), Chinese herb sho-saiko-to (or Xiao-Shai-Hu-Tang)	

Should subjects have a need to initiate treatment with any excluded concomitant medication, including herbal/natural products/therapies, and over the counter medications, the Gilead Sciences Medical Monitor must be consulted prior to initiation of the new medication. In instances where an excluded medication is initiated prior to discussion with the Sponsor, the investigator must notify Gilead Sciences as soon as he/she is aware of the use of the excluded medication.

5.5. Accountability for Tenofovir Alafenamide (TAF), Tenofovir Disoproxil Fumarate (TDF) and Matched Placebos

The investigator or designee (i.e., pharmacist) is responsible for ensuring adequate accountability of all used and unused investigational medicinal product (IMP) bottles. This includes acknowledgement of receipt of each shipment of IMP (quantity and condition). All used and unused IMP bottles dispensed to subjects must be returned to the site.

Investigational product accountability records will be provided to each study site to:

- Record the date received and quantity of IMP bottles
- Record the date, subject number, subject initials, the IMP bottle number dispensed
- Record the date, quantity of used and unused IMP bottles returned, along with the initials of the person recording the information

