4.2. Inclusion Criteria

Subjects must meet all of the following inclusion criteria to be eligible to participate in the study:

- 1) Must have the ability to understand and sign a written informed consent form; consent must be obtained prior to initiation of study procedures
- 2) Adult male and non-pregnant, non-lactating female subjects, ≥18 years of age based on the date of the screening visit. A negative serum pregnancy test at Screening is required for female subjects of childbearing potential (as defined in Appendix 5).
- 3) Documented evidence of chronic HBV infection previously (e.g., documented HBsAg positive for more than 6 months)
- 4) Maintained on TDF 300 mg QD for at least 48 weeks, and as monotherapy for CHB for at least 24 weeks prior to screening and with viral suppression (HBV DNA < LLOQ by local laboratory assessment) for a minimum of 12 weeks prior to Screening, and including a Screening HBV DNA value of < 20 IU/mL (by central laboratory)
- 5) Estimated creatinine clearance ≥ 50 ml/min (using the Cockcroft-Gault method) based on serum creatinine and actual body weight as measured at the Screening evaluation, as follows:

(Note: multiply estimated rate by 0.85 for women)

- 6) Normal ECG (or if abnormal, determined by the Investigator not to be clinically significant)
- 7) Must be willing and able to comply with all study requirements

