8.6. Efficacy Analysis

8.6.1. Primary Analysis

The primary analysis will be performed when the last subject has completed Week 48 assessments or discontinued prematurely. The primary analysis will consist of a non-inferiority evaluation of efficacy of TAF versus TDF, with respect to the proportion of subjects with HBV DNA \geq 20 IU/mL at Week 48 (as defined by the modified FDA snapshot Algorithm). It will be concluded that TAF is not inferior to the TDF if the upper bound of the two-sided 95% confidence interval of the difference between treatment arms (TAF arm – TDF arm) in the response rate is less than 4% (i.e., a margin of 4% is applied to non-inferiority assessment). The 95% confidence interval will be constructed using the normal approximation method based on stratified Mantel-Haenszel proportions, where stratification factors are HBeAg status (HBeAg positive or negative) and age (\geq 50 or < 50 years).

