8.6.1.1. Modified US FDA-Defined Snapshot Alogrithm

The US FDA-defined snapshot algorithm, developed for HIV-1 clinical trials, has been modified for use in HBV {U. S. Department of Health and Human Services 2015} using on-treatment HBV DNA values of < 20 IU/mL and ≥ 20 IU/mL.

The analysis window at Week 48 is defined as from Study Day 294 to Study Day 377, inclusive. All HBV DNA data collected on-treatment will be used in the snapshot algorithm. Virologic outcome will be defined as the following categories:

- **HBV DNA < 20 IU/mL:** this includes subjects who have the last available on-treatment HBV DNA < 20 IU/mL in the Week 48 analysis window
- HBV DNA \geq 20 IU/mL: this includes subjects who
 - 1) Have the last available on-treatment HBV DNA ≥ 20 IU/mL in the Week 48 analysis window, or
 - 2) Do not have on-treatment HBV DNA data available in the Week 48 analysis window and
 - a) Discontinue study drug prior to or in the Week 48 analysis window due to lack of efficacy, or
 - b) Discontinue study drug prior to or in the Week 48 analysis window due to reason other than lack of efficacy and have the last available on-treatment HBV DNA ≥ 20 IU/mL

- No Virologic Data in the Week 48 Analysis Window: this includes subjects who do not have on-treatment HBV DNA data available in the Week 48 analysis window for any of the following reasons:
 - 1) Discontinuation of study drug prior to or within the Week 48 analysis window due to reasons other than lack of efficacy and the last available on-treatment HBV DNA value is < 20 copies/mL, or
 - 2) Missing data within the window but who are on study drug treatment

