8.9. Sample Size

With respect to the primary efficacy endpoint of proportion of suppressed subjects with HBV DNA \geq 20 IU/mL (current assay LLOQ), as determined by the modified US FDA-defined snapshot algorithm, at Week 48, when the sample sizes are 230 (TAF 25 mg arm) and 230 (TDF 300 mg arm), a two-group, large-sample normal approximation test of proportions with a one-sided 0.025 significance level will have 80% power to establish non-inferiority of TAF to TDF. It is assumed that both treatment arms will have subjects who have HBV DNA \geq 20 IU/mL (as defined by the modified US FDA-defined snapshot algorithm) at a rate of 2.4% at Week 48 (based on the rates of suppressed subjects having HBV DNA \geq 29 IU/mL [the LLOQ of assay during those studies] after 48 weeks of treatment from the combined data of studies GS-US-174-0102 and GS-US-174-0103 with the ratio of HBeAg- to HBeAg+ subjects assumed to be 2:1), with a non-inferiority margin of 4%.

The proposed sample size (n = 230 for the TAF 25 mg arm, n = 230 for the TDF 300 mg arm) also provides > 99% power to detect a 1.81% difference in the percentage change from baseline in hip BMD at Week 48 (assuming a 1.47% [SD 2.71%] change from baseline in TAF 25 mg arm and -0.34% [SD 2.83%] change from baseline in the TDF 300 mg arm, with a two-sided $\alpha = 0.05$); a > 99% power to detect a 2.00% difference in the percentage change from baseline in spine BMD at Week 48 (assuming a 1.56% [SD 3.84%] change from baseline in the TAF 25 mg arm and -0.44% [SD 4.14%] change in the TDF 300 mg arm, with a two-sided $\alpha = 0.05$); a 97% power to detect a 4.9 mL/min difference in the change from baseline in eGFR_{CG} at Week 48 (assuming a 1.3 mL/min [SD 13.2] change from baseline in the TAF 25 mg arm and -3.6 mL/min [SD 13.0] change from baseline in the TDF 300 mg arm, with a two-sided $\alpha = 0.05$). These assumptions were derived from an HIV switch study (GS-US-292-0109) due to the unavailability of switch data from TAF HBV studies.

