6.2.2. Analysis Methods for Secondary Efficacy Endpoints

The primary analysis of the proportion of subjects in the Full Analysis Set with HBV DNA ≥ 20 IU/mL (as determined by the modified US FDA-defined snapshot algorithm {U. S. Department of Health and Human Services 2015}) will be repeated for the Week 96 endpoint using the FAS. The Week 96 analysis window is defined as from Study Day 589 to Study Day 840, inclusive.

The analyses for the other secondary efficacy endpoints will be conducted using the FAS. All secondary efficacy endpoints involving proportions will be analyzed from baseline to Week 96 using both the Missing Failure (M F) approach and the Missing Excluded (M E) approach, unless otherwise specified. In the M E approach, all missing data will be excluded in the computation, and in the M F approach, all missing data will be treated as failures and included in both the numerator and denominator. P-values will be calculated using the CMH test stratified by baseline HBeAg status (HBeAg-positive or HBeAg-negative) and age (< 50 or ≥ 50 years), and the proportion difference between the 2 treatment groups and the associated 95% CIs will be calculated based on the stratum-adjusted MH proportion.

The change from baseline in \log_{10} (HBsAg) (IU/mL), both overall and by baseline HBeAg status, and ALT will be summarized by visit using observed data (ie, missing data will be excluded). The p-value, differences in change from baseline in \log_{10} (HBsAg) (IU/mL) and ALT between the 2 treatment groups and the associated 95% CI will be constructed using analysis of variance (ANOVA) models, including treatment group, baseline HBeAg status (HBeAg-positive or HBeAg-negative), and age (< 50 or \geq 50 years) as fixed effects in the model. For the analysis of change from baseline in \log_{10} (HBsAg) (IU/mL) by baseline HBeAg status, only treatment group and age (< 50 or \geq 50 years) will be included as fixed effects in the model.

In addition, the proportion of subjects in the FAS with HBV DNA < 20 IU/mL, the proportion of subjects with normal ALT by the central laboratory and 2018 AASLD criteria (ULN is 35 U/L for males and 25 U/L for females) using the M E approach, and the mean change from baseline in log10 (HBsAg) (IU/mL) and ALT (U/L) will be plotted with 95% CI over time using observed data from baseline to Week 96.

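### The snapshot scores success without regard to non-study HBV antivirals, and Protocol Section 5.4 does not state their status during study treatment

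*Protocol*

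**What the plan says.** **Medication rules.** Protocol 5.4 introduces its list with "The following medications are excluded while subjects are participating in the study". The five bullets cover investigational agents, nephrotoxic agents, probenecid, agents that impair renal function or compete for tubular secretion, and chemotherapy, steroids and immune-acting drugs. Table 5-1 adds anticonvulsants, antimycobacterials and herbal products. No entry names entecavir, lamivudine, adefovir, telbivudine, or TDF or TAF from outside the study. Inclusion criterion 4 requires TDF "as monotherapy for CHB for at least 24 weeks prior to screening", which looks backward only.

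**Rebound and alternative therapy.** Protocol 6.8 answers a rebound with a repeat test, a resistance sample, a pill count and adherence counselling. Other HBV therapy appears only for subjects who have stopped study drug (Protocol 3.1, 6.4.2 and 7.5.5.1).

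**Scoring.** Protocol 8.6.1.1 says "All HBV DNA data collected on-treatment will be used in the snapshot algorithm". Success is a last available on-treatment value below 20 IU/mL in the Week 48 window. SAP 3.6.2 defines on-treatment by study-drug dates alone, for example up to the last blinded dose plus 3 days. The discontinuation branches apply only when the window holds no on-treatment value. SAP 6.2.2 says that the primary analysis "will be repeated for the Week 96 endpoint using the FAS". SAP 4.1 counts subjects who started another HBV therapy as a disposition category, and no efficacy rule uses that count.

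**The concern.** The trial asks whether TAF maintains suppression as well as continued TDF. A value below 20 IU/mL bears on that question only if the assigned drug produced it. Under the stated rule, a subject can lose suppression, have a second HBV drug added while blinded dosing continues, re-suppress, and enter the analysis as maintained suppression.

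In a non-inferiority test this error is anti-conservative. If failures are masked in both arms in proportion to how often they occur, the observed difference shrinks and the interval narrows. If TAF were truly worse, its excess failures are the ones most likely to disappear. Few events are expected, so a handful of reclassified subjects could decide the result.

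**Working it through.** **Inputs.** Protocol 8.9: 230 per arm, failure "at a rate of 2.4% at Week 48" in both arms, one-sided 0.025, 80% power. Protocol 8.6.1: "a margin of 4% is applied to non-inferiority assessment", judged on the upper bound of the two-sided 95% interval for TAF minus TDF.

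**The plan's own figure.** Standard error = √(2 × 0.024 × 0.976 / 230) = 0.01427. Power = Φ(0.04 / 0.01427 − 1.96) = Φ(0.843) = 80.0%. The stated power and sample size are reproduced.

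**Weight of one subject.** Expected failures are 0.024 × 230 = 5.5 per arm. One subject is 1/230 = 0.43 percentage points, about 11% of the margin.

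**Upper bounds.** With a and b failures out of 230, p = a/230 and q = b/230, the bound is p − q + 1.96 × √[p(1−p)/230 + q(1−q)/230]. This is unstratified; the plan uses stratified Mantel-Haenszel proportions, so the figures are illustrative.

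| TAF vs TDF failures | Upper bound | Below 4%? |
|---|---|---|
| 8 vs 5 | 4.33% | no |
| 7 vs 5 | 3.78% | yes |
| 7 vs 4 | 4.09% | no |
| 8 vs 6 | 4.01% | no |
| 7 vs 6 | 3.46% | yes |

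Starting from 8 vs 5, masking one TAF failure changes the conclusion, while masking one failure in each arm (7 vs 4) does not. Symmetric masking is not always harmless: from the borderline 8 vs 6, one in each arm leads to 7 vs 5, which passes.

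**Error rate under assumed masking.** The documents give no rate of add-on therapy, so the masked share r of failures is an assumption, shown over a range. True rates are set at the margin (TAF 6.4%, TDF 2.4%). The chance of a false non-inferiority claim, by exact binomial enumeration of the same unstratified interval, is:

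| r | Masked in both arms | Masked in TAF only |
|---|---|---|
| 0 | 3.2% | 3.2% |
| 10% | 5.2% | 6.5% |
| 25% | 10.7% | 16.8% |
| 50% | 34.5% | 55.0% |

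The r = 0 row exceeds 2.5% because of the normal-approximation interval itself, not because of masking.

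**The case against.** The strongest reply is that the protocol describes no add-on pathway. Section 6.8 offers retesting and counselling, Section 6.6 lists therapeutic failure as a reason to stop study drug, and other HBV therapy follows that stop. On that route later HBV DNA is off-treatment, and stopping for lack of efficacy with no value in the window is already a failure. This stands: mis-scoring requires a site to add therapy while study drug continues. A reader might infer that the protocol plans or endorses such rescue; it does not.

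A reader might also infer that continued use of personal TDF is permitted. The design contrasts a switch to TAF with sponsor-provided TDF (Protocol 3.1 and 5.3), and extra TDF would depart from the assigned regimen. The gap is that this is nowhere stated. Reading personal TDF into the nephrotoxic bullet does not work well: that bullet applies from at least 30 days before Baseline, when subjects must be on TDF, and it would not reach entecavir or lamivudine. Interferon may fall under immunomodulating agents. In any case, calling such use a deviation does not change how the snapshot scores it.

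Three further limits stand:
- The rule does not accept any on-treatment value below 20 IU/mL. It takes the last one in the window.
- Blinding gives no reason to assume that masking falls only in the TAF arm.
- SAP 6.1.1 refers to a separate Week 48 SAP for the details of the primary analysis. It was not available and may contain a handling rule.

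**Conclusion.** The point holds as a gap in the stated scoring rule. Section 5.4 leaves the status of non-study HBV antivirals during study treatment unstated, and neither the protocol's snapshot nor its Week 96 repeat in the SAP takes them into account. An add-on-rescued rebound would count as success, and the resulting bias is toward non-inferiority. One rescored TAF subject can change the conclusion near the boundary; one in each arm may or may not.

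The size rests on assumed frequencies and an unstratified interval. A reader might conclude that the Week 48 result was in fact distorted. The documents do not support that: they report no such use, and the Week 48 SAP is unseen. The gap is worth closing because the correction is cheap and few failures are expected.

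**What to change.** **Analysis rule.** In Protocol 8.6.1.1 and SAP 6.2.2, state that HBV DNA collected after the start of any non-study anti-HBV drug, identified from the concomitant medication eCRF, cannot support < 20 IU/mL. Classify the subject by the last on-treatment value before that start, following the existing logic. Where the window holds no usable value, a last earlier value ≥ 20 IU/mL, or a drug started for lack of efficacy, is a failure; otherwise the category is No Virologic Data.

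**Sensitivity analysis.** Score all such subjects as failures and report their number by arm. This should not be the main rule. It departs from the snapshot's own treatment of non-efficacy cases, and a TDF-arm subject taking personal TDF would become a TDF failure, which lowers TAF minus TDF and favours non-inferiority.

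**Reconciliation.** Protocol 5.3, 5.4, 6.8 and 8.6.1.1 must be reconciled so that they state the status of non-study HBV therapy during study treatment. Which clinical rule applies is for the sponsor to settle.

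**Cost.** One branch in the algorithm and one extra table. Protocol 5.4 already requires concomitant medications to be recorded, and the planned 230 per arm does not change. The observed failure or no-data rate may rise slightly.
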